General medical history	X	X ²⁴	X ²⁴												
Prior and concomitant medications	X	X	X	X	X	X	X	X	X	X	X	X	X		
Physical examination	X	X												X	
SOL-116 administration ⁶			X					X	X	X					
Injection site reactions			X ¹⁶	X	X			X ¹⁶	X ¹⁶	X ¹⁶					
12-lead ECG ⁷	X	X	X					X ¹⁷	X ¹⁷	X ¹⁷				X	
3-lead ECG (telemetry) ⁸			X												
Pregnancy testing ⁹	X	X						X	X	X				X	
Serology	X														
Serum FSH (postmenopausal women only)	X														
Blood sampling for SOL-116 PK			X ¹⁸	X	X	X	X	X ¹⁹	X ¹⁹	X ²⁰	X	X	X		
Blood sampling for immunogenicity			X ¹⁹					X ¹⁹	X ¹⁹	X ¹⁹		X ²¹	X		
Blood sampling for BSSL			X ¹⁸	X	X	X	X	X ¹⁹	X ¹⁹	X ²⁰	X	X	X		

Study Period	Screening	Treatment period										FU/EOS		
		Visit 1 ¹	Visit 2 ²			Visit 3	Visit 4 ³	Visits 5-6	Visit 7 (dosing day) ⁴	Visit 8 (dosing day) ⁴	Visit 9 (dosing day)	Visits 10-11	Visits 12-17	
Visit	Visit 1 ¹		Visit 2 ²			Visit 3	Visit 4 ³	Visits 5-6	Visit 7 (dosing day) ⁴	Visit 8 (dosing day) ⁴	Visit 9 (dosing day)	Visits 10-11	Visits 12-17	Visit 18
Assessments / Study days (visit windows in days)	Day -28 to Day -2	Day -1	Day 1	Day 2	Day 4 (72 hrs) (±1)	Day 8 (±1)	Days 11 and 15 (±1)	Day 29 (±1)	Day 57 (±3)	Day 85 (±3)	Day 86 and 88	Days 92, 95, 99, 113, 140, 154 (±3)	Day 169 (±5)	
Blood sampling for cytokine and chemokine panel			X ¹⁹		X	X		X ¹⁹	X ¹⁹	X ¹⁹	X ²²	X ²³	X	
Blood sampling for future exploratory analysis ¹⁰			X ¹⁹								X		X ¹⁵	X
Urine drugs of abuse and cotinine screen	X	X ¹⁹												
Alcohol test	X	X ¹⁹							X ¹⁹	X ¹⁹	X ¹⁹			
Serum biochemistry, lipid status, hematology, coagulation, urinalysis ¹¹	X	X ¹⁹			X	X		X ¹⁹	X ¹⁹	X ¹⁹	X ²²	X ¹⁵	X	
Baseline symptoms	X	X ²⁴	X ²⁴											
Ambulant visit	X				X	X	X	X	X	X	X	X	X	X
Residence in clinic ¹²		X	X	X										
AEs/SAEs reported/questions ¹³			X	X	X	X	X	X	X	X	X	X	X	X

Abbreviation: ADA, anti-drug antibodies; AEs, adverse events; BSSL, bile salt-stimulated lipase; CCP, cyclic citrullinated peptide; CRP, C-reactive protein; ECG, electrocardiogram; ESR, erythrocyte sedimentation rate; FSH, follicle stimulating hormone; PK, pharmacokinetics.

1. Screening can be divided over 2 visits.
2. Spare subjects not immediately included in the study may be kept in the clinic until it is decided whether these subjects are to be included. If subjects are included > 48 hours after admission in the clinic on Day -1, the Day -1 assessments have to be repeated.
3. If the clinic visit is extended up to and including Day 6, Visit 4 will not take place. In that case, all assessments including blood sampling scheduled for Visit 4 will be performed on Day 6, at the discretion of the Investigator.
4. Study site should make a **phone follow-up with subject approximately 3 to 7 days after dose** to follow up adverse events and/or medication.
5. Not to be performed when this assessment was done within 3 weeks prior to dosing and result is available.
6. The PI must review Day -1 safety lab results prior to dosing.
7. Triplicate at Screening and on Day -1. On Day 1: 1 and 4 hours post-dose.
8. From 1 hour pre-dose until 6 hours post-dose.
9. Serum at Screening, urine at all other timepoints.
10. Only collected and analysed when the subject has given consent for the collection and future analysis of this sample in the informed consent form. Pre-dose on Day 1 and Days 85, 92 and 169.
11. Fasting glucose determined at Screening only. Lipid status determined only at Screening and Day 169 only (10 hours' fasting at both occasions). No pancreatic lipase on Day 92.

12. If medically indicated and/or based on emerging data, the clinic stay may be extended up to Day 7.
13. Starting from first study drug administration.
14. On Day 1: Prior to dosing and 1 and 4 hours post-dose. After the other doses: Prior to dosing and 4 hours post-dose.
15. Day 92 only
16. Assessed for four (4) hours after each injection and thereafter as needed.
17. Prior to dosing and 4 hours post-dose.
18. Pre-dose, 4 and 24 hours post-dose
19. Pre-dose only.
20. Pre-dose and 4 hours post dose.
21. Day 113 only.
22. Day 88 only
23. Days 92 and 113 only.
24. Up until first study drug administration.

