	
13. Subjects/patients who are currently enrolled in or have recently participated in another interventional clinical study defined as having received the last intervention within 90 days or 5 half-lives of the study drug (whichever is longer) prior to dosing (Parts 1 and 2) vs. prior to first dosing (Part 3) of the study drug.14. History or known hypersensitivity or allergy, or any form of allergic reactions to any excipients in the study drug or to humanized or murine monoclonal antibodies (or immunoglobulins).15. Receipt of a vaccine within 4 weeks (COVID-19 vaccine within 6 weeks) prior to dosing and/or the intention to receive a vaccine during the study. Deviation from this should be judged by the Investigator and in dialogue with the Sponsor.16. Recent confirmed COVID-19 infection, with less than 6 weeks between recovery and dosing of study drug.17. Blood or plasma donation within 3 months of enrolment.18. Positive urine drug screen or alcohol test at Screening or on Day -1.19. History of drug or alcohol abuse, at the discretion of the Investigator, within past 12 months prior to Screening.20. The subject currently smokes or uses nicotine-containing products. Former smokers will be eligible, provided they have not smoked for at least 1 month prior to Screening. Positive cotinine test results at Screening or on Day -1 are reason for exclusion. Such positive test results can be repeated once to exclude environmental influence on the subject.21. A positive pregnancy test or lactation at Screening or on Day -1. 
The following exclusion criteria are only applicable for RA patients:
 
22. Intra-articular or systemic corticosteroid injection within 4 weeks prior to dosing.23. Current or expected need of other immunosuppressant medication except MTX and/or intra-articular corticosteroid injections.24. Known Gilbert's syndrome or Screening laboratory values indicating Gilbert's syndrome.
SAFETY / TOLERABILITY PARAMETERS	
The following are defined as safety/tolerability parameters:
 
• Clinical laboratory evaluations;• Injection site reactions;• Adverse events (AEs);• Immune reactions (e.g. hypersensitivity, cytokine release syndrome, immunogenicity);• Vital signs;

	
 Physical examination; ECGs (3-lead telemetry and 12-lead ECGs); Concomitant medications/therapy.

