13. On Day 1 prior to dosing, and at 1, 4, 8, 24 (Day 2), 48 (Day 3, optional) and 72 hours (Day 4) post-dose.
14. On Day 1 prior to dosing. Based on emerging data, collection time points may be updated.
15. Only collected and analysed when the patient has given consent for the collection and future analysis of this sample in the informed consent form.
16. Fasting glucose and lipid status determined at Screening, pre-dose on Day 1, Day 14 and Day 35. α -tocopherol status determined pre-dose on Day 1, Day 14 and Day 35 only. S-calprotectin and hsCRP determined prior to dosing and 4 hours post-dose on Day 1, on Day 2, on Day 4, on Day 21, on Day 49 and on Day 90. Subjects should be fasting for at least 4 hours prior to blood sampling at Screening, and 10 hours prior to blood sampling on Day 1, Day 14 and Day 35. Rheumatoid factor and anti-CCP antibodies only at Screening. Urinalysis only at Screening, on Day -1, on Day 2, on Day 8, on Day 14, on Day 21, and on Day 90. At Screening, laboratory assessments may be repeated once, at the discretion of the Investigator.
17. If medically indicated and/or based on emerging data, the clinic stay may be extended up to Day 7.
18. Starting from study drug administration.
19. Prior to dosing and 4 hours post-dose.
20. 4 hours post-dose.
21. Up until study drug administration.
22. Spare patients not immediately included in the study may be kept in the clinic until it is decided whether these patients are to be included. If subjects are included > 48 hours after admission in the clinic on Day -1, the Day -1 assessments have to be repeated.

Table 5-3: Visit and Assessment Schedule for Repeated Dosing Part (every Q4W dosing) – Part 3

Study Period	Screening	Treatment period													FU/EOS
		Visit 1 ¹	Visit 2 ²		Visit 3	Visit 4 ³	Visits 5-6	Visit 7 (dosing day) ⁴	Visit 8 (dosing day) ⁴	Visit 9 (dosing day)	Visits 10-11	Visits 12-17			
Assessments / Study days (visit windows in days)	Day -28 to Day -2	Day -1	Day 1	Day 2	Day 4 (72 hrs) (±1)	Day 8 (±1)	Days 11 and 15 (±1)	Day 29 (±1)	Day 57 (±3)	Day 85 (±3)	Day 86 and 88	Days 92, 95, 99, 113, 140, 154 (±3)	Day 169 (±5)		
Informed consent	X														
Eligibility criteria	X	X													
Randomization			X												
Demographics	X														
Height	X														
Weight	X	X								X	X	X			
BMI	X														
QuantiFERON® test ⁵	X														
Vital signs (blood pressure, pulse rate, temperature)	X		X ¹⁴	X	X	X		X ¹⁴	X ¹⁴	X ¹⁴	X	X ¹⁵	X		

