The cohort with RA patients (Cohort 7) will be run after the completion of all cohorts with healthy subjects. The dose level of Cohort 7 will be determined based on the safety and PK results of all preceding cohorts and will not exceed that of the already given dose levels in healthy subjects. There should be at least 24 hours between administration of SOL-116 and the preceding methotrexate (MTX) dose and at least 24 hours between administration of SOL-116 and the subsequent MTX dose.

Sentinel dosing will be employed. Thus, initially 1 patient will receive SOL-116 and 1 patient will receive placebo. The remaining 6 subjects of the cohort can be dosed at least 48 hours after dosing, provided no clinically significant safety issues, as judged by the Investigator, are noted in the 48 hours after dosing of the initial 2 patients of the cohort.

Please refer to [Table 5-2](#) for an overview of ambulatory visits and residence in the clinic.

Part 3

The multiple dosing part will be in healthy subjects where, in the first multiple dosing cohort, each subject will receive a total of four doses every fourth week (Q4W): at baseline (D1) and Days 29, 57 and 85. With a dose interval of 28 days, it is estimated that with the half-life of SOL-116 (assessed in the SAD) concentrations at, or close to, steady state will be reached after the fourth dose.

Eligibility will be assessed during a screening period of up to 28 days. For the first dose, subjects will check into the clinic one day prior to dosing (Day -1). On Day 1, all subjects will receive SOL-116 or placebo. Subjects will be released from the clinic on Day 2, after all required study procedures are completed and if medically justified. If medically indicated and/or based on emerging data, the clinic stay may be extended up to Day 7. Subjects will return to the clinic for 15 ambulant visits up to Day 154. Subjects will return to the clinic on Day 169 for an EOS/follow-up visit. After the second and third dose, a phone contact will be made (3 to 7 days after the dose) with the subject to ensure no new adverse events or if new medication has been added.

Up to two multiple dosing cohorts of 8 healthy subjects (6 active, 2 placebo) (Cohorts MD1 and MD2) are planned, i.e. in total up to 16 subjects will be randomized and dosed.

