8.7.2 Dose Escalation Stopping Criteria

- One (1) or more subjects who receive SOL-116 experience a SAE which is considered to be related to the study medication.
- Two (2) or more subjects who receive SOL-116 have QTc prolongation, defined as an average absolute (regardless of baseline value) QTcF >500 msec or an increase of QTcF >60 msec above baseline, confirmed by repeated ECG after at least 5 minutes, and determined post-dose.
- Two (2) or more subjects who receive SOL-116 exhibit hypotension, defined as resting supine diastolic blood pressure <40 mmHg, an asymptomatic or symptomatic fall in systolic blood pressure to below 80 mmHg, persisting for at least 10 minutes on repeated assessment.
- Two (2) or more subjects who receive SOL-116 exhibit hypertension, defined as an increase in resting systolic blood pressure to above 180 mmHg, persisting for at least 10 minutes, or an increase in resting diastolic blood pressure to above 105 mmHg, persisting for at least 10 minutes.
- Two (2) or more subjects who receive SOL-116 exhibit tachycardia, defined as resting supine heart rate >130 beats per minute, persisting for at least 10 minutes.
- Two (2) or more subjects who receive SOL-116 exhibit symptomatic bradycardia, defined as heart rate <40 beats per minute, or asymptomatic bradycardia, defined as resting supine heart rate <30 beats per minute while awake, persisting for at least 10 minutes.
- One (1) or more subjects who receive SOL-116 fulfills Hy's law, defined as aspartate aminotransferase (AST) or alanine aminotransferase (ALT) $\geq 3 \times$ upper limit of normal (ULN) and total bilirubin $\geq 2 \times$ ULN, in the absence of a significant increase in alkaline phosphatase (ALP) and in the absence of an alternative diagnosis that explains the increase in total bilirubin (confirmed by repeating within 24 hours).
- Two (2) or more subjects who receive SOL-116 exhibit ALT, total bilirubin, or ALP $>3 \times$ ULN accompanied by significant increase in other liver function test (confirmed by repeating within 24 hours).
- Two (2) or more subjects who receive SOL-116 exhibit renal toxicity, defined as serum creatinine $\geq 1.5 \times$ ULN (confirmed by repeating within 24 hours).
- Two (2) or more subjects who receive SOL-116 exhibit hematologic toxicity, defined as one or more of the following (confirmed by repeating within 24 hours):
 - Leukocyte count $<2.5 \times 10^9/L$
 - Neutrophil count $<1.0 \times 10^9/L$

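### Part 3 schedules no vital sign, ECG or telemetry between dosing and 4 hours at doses 2 to 4, so acute asymptomatic changes on re-exposure have no scheduled value and the 1-hour change cannot be compared with dose 1

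*Protocol*

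**What the plan says.** In the first multiple-dose cohort, "each subject will receive a total of four doses every fourth week (Q4W): at baseline (D1) and Days 29, 57 and 85" (protocol 8.2). On size, "Up to two multiple dosing cohorts of 8 healthy subjects (6 active, 2 placebo) (Cohorts MD1 and MD2) are planned".

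In Table 5-3 the vital-signs row carries footnote 14 on all four dosing days: "On Day 1: Prior to dosing and 1 and 4 hours post-dose. After the other doses: Prior to dosing and 4 hours post-dose". Footnotes 7 and 17 step the 12-lead ECG down in the same pattern, and the telemetry row is marked on Day 1 only. Injection sites are followed at every dose: "Assessed for four (4) hours after each injection and thereafter as needed" (footnote 16). Anti-drug antibodies (ADA) are sampled before each dose, then on Days 113 and 169.

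The Part 3 primary objective is the safety and tolerability of multiple dosing (7.2). Vital signs, ECG and immune reactions are all primary endpoints (8.1.1), and hypersensitivity and cytokine release syndrome are named as examples of immune reactions (8.11.2).

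SAP 7.7.3.5 summarises vital signs at each time point collected under the protocol. SAP 7.1 keeps extra measurements out of the descriptive statistics and shows them in listings only. It also takes baseline as the last value before the first study drug intake. The visible text gives no reason for dropping the 1-hour reading.

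**The concern.** ADA induced by treatment cannot exist at dose 1 but can at doses 2 to 4. The early objective readings are therefore scheduled at the one dose where this mechanism is excluded and left out at the doses that Part 3 was added to study. A short-lived fall in blood pressure or rise in pulse after a later dose would reach the primary safety tables only if it were still present at 4 hours.

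Symptom reporting does not fully replace a measurement. The hypotension criterion in 8.7.2 expressly counts falls without symptoms, and the tachycardia criterion, whose duration is in minutes, mentions no symptoms: "Two (2) or more subjects who receive SOL-116 exhibit tachycardia, defined as resting supine heart rate >130 beats per minute, persisting for at least 10". An ad hoc reading would be listed but not summarised, and placebo subjects would have no matching scheduled value.

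**Working it through.** The documents give no sample size calculation, power or error rate, so there is no stated figure to reproduce. The check is a reading of the schedule followed by a count.

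**1. Schedule side by side (Table 5-3 and footnotes)**

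| Assessment | Dose 1 (Day 1) | Doses 2–4 (Days 29, 57, 85) |
|---|---|---|
| Vital signs (footnote 14) | pre-dose, 1 h, 4 h | pre-dose, 4 h |
| 12-lead ECG (footnotes 7, 17) | 1 h, 4 h | pre-dose, 4 h |
| Telemetry (footnote 8) | 1 h before to 6 h after | none |
| Cytokine panel (footnote 19) | pre-dose | pre-dose |
| Injection sites (footnote 16) | followed for 4 h | followed for 4 h |

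At doses 2 to 4 the first scheduled vital sign or ECG after dosing is at 4 h. After doses 2 and 3 the next contact is a phone call 3 to 7 days later (footnote 4), so the 4 h reading is the only post-dose vital sign before the next dosing visit. After dose 4, vital signs are also taken on Days 86 and 88.

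**2. Count for MD1 (6 active, 2 placebo, 4 doses)**

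- Active dosings: 6 × 4 = 24.
- Active dosings with a 1 h reading: 6 × 1 = 6.
- Active re-exposures: 6 × 3 = 18, all without a 1 h reading. 18/24 = 75%.
- Including placebo: 8 × 3 = 24 re-exposures, all without one.

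**3. Two cohorts, if MD2 keeps the four-dose schedule** (an assumption, because 8.2 lets its frequency change): 12 of 48 active dosings have a 1 h reading, and 36 of 36 active re-exposures have none.

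**4. Effect of adding the 1 h reading.** Scheduled 1 h readings on active drug in MD1 would rise from 6 to 24. Each active subject would then have three within-subject comparisons with dose 1. The longest interval without a reading in the first 4 hours would fall from 4 h to 4 − 1 = 3 h.

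**5. Illustration with assumed rates.** Let p be the chance per active subject of an event on re-exposure that is visible at 1 h and gone by 4 h. The documents give no value for p. The chance of at least one such event among 6 subjects is 1 − (1 − p)^6:

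| p | At least one in 6 |
|---|---|
| 5% | 0.27 |
| 10% | 0.47 |
| 20% | 0.74 |
| 30% | 0.88 |

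The current schedule would give no scheduled vital-sign value for any such event.

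**The case against.** The strongest reply is that this is a deliberate step-down after first exposure. Vital signs, ECG and telemetry are reduced together, and nothing in the documents contradicts footnote 14. Part 1 reported no clinically relevant changes in vital signs, ECG or telemetry in 40 subjects at single doses up to 6.075 mg/kg, above the 3.0 mg/kg of MD1 (6.1.3). Exposure also peaks late: 28 days is described as Tmax plus one half-life, and the half-life is about 19 days, so Tmax is near 28 − 19 = 9 days. Parts of the risk analysis are redacted, so a rationale may exist out of view.

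Much of this stands. There is no internal contradiction, and the gap concerns acute reactions after injection, not effects at peak concentration. The Part 1 data are single-dose, however, and cannot speak to reactions that depend on antibodies formed after an earlier dose.

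A reader might infer that early reactions on re-exposure go unobserved, or that later doses cannot be compared with dose 1 at all. The documents do not support that. Pre-dose and 4 h values exist at all four doses, injection sites are followed for 4 hours, AEs are asked about at each dosing visit, and clinically significant abnormal vital signs must be reported as AEs (9.1.1).

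A reader might also infer that the 8.7.2 stopping criteria cannot be triggered by events before 4 h. They are not limited to scheduled readings. Conversely, a single 1 h value could prompt a repeat but could not by itself show 10 minutes' persistence.

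It is also fair that nothing in the documents identifies 1 h as the most informative time. A change at 15 to 30 minutes, or at 2 to 3 hours, could still fall between readings.

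**Conclusion.** The point holds in a limited form. At all 18 active re-exposures in MD1, no vital sign, ECG or telemetry is scheduled between dosing and 4 h. What is lost is a scheduled value for an asymptomatic change that starts and resolves in that interval, and any comparison of the 1 h change with dose 1. The figure of 36 re-exposures over two cohorts rests on MD2 keeping the MD1 schedule.

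The count gives the extent of the gap, not the likelihood of a missed event; the documents give no event rate. This is a gap in measurement and comparability in a primary endpoint. It is neither an error of arithmetic nor a conflict between passages. It merits action because it is cheap to narrow, using times the protocol already contains.

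**What to change.** - **Protocol.** For any remaining MD1 doses and for MD2, apply the Day 1 vital-sign times already in footnote 14 (pre-dose, 1 h, 4 h) to every dosing day. If the reduced schedule is kept, state the reason.
- **SAP 7.7.3.5 and Table 14.3.6.** Summarise the 1 h and 4 h changes by dose number against that dose's own pre-dose value. The SAP 7.1 baseline precedes the first dose, so it mixes drift since Day 1 with the acute change at doses 2 to 4.
- **Study report.** For doses already given without a 1 h reading, state that acute vital-sign changes before 4 h on re-exposure were not systematically measured.

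**Cost.** Under the MD1 schedule this is one extra non-invasive reading per later dosing visit: three per subject, or 8 × 3 = 24 per full cohort. Subjects are already on site for the 4 h assessments. Section 12.1.1.2 lists changes to study assessments as substantial, so an amendment and its approvals are needed. Section 8.7.1 lets the SRC add safety time points, but its Part 3 review uses data to 28 days after the last dose, so that route realistically helps only MD2. Part 3 was already under way (6.1.3), so MD1 may end with mixed schedules. The 1 h tables should then show the number of subjects measured at each dose.

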6 INTRODUCTION AND RATIONALE

6.1 Background

Rheumatoid arthritis (RA) is a chronic autoimmune inflammatory joint disease characterized by varying numbers of swollen, stiff and painful joints typically in hands and feet, but any joint may be affected. With time, erosion of joints and bone results in varying degree of disability and loss of quality of life. RA may also have systemic manifestations affecting other organs, e.g., skin, heart, lungs and/or eyes causing severe complications. The etiology of the disease is not fully understood but the expert opinion is that a combination of genetic predisposition and environmental factors as trigger is needed. Examples of triggers are cigarette smoking, infections, and trauma. The global prevalence of RA is 0.3% to 1% with significant variation between populations and the disease is threefold more common among women than men [1]. It affects all age groups but the most common age at onset is 40-60 years [2]. RA is a heterogeneous disease with substantial variation between individuals both with respect to number of joints and organs affected and the activity of the disease, something that is also reflected on the cellular and molecular level. This in turn is likely part of the explanation why a substantial proportion of the RA patients do not respond satisfactorily to current treatment alternatives, and why there is still a great medical need for new treatment alternatives [3].

6.1.1 Product Characteristics

The intended product SOL-116 is a humanized monoclonal anti-Bile Salt-Stimulated Lipase (BSSL) antibody of the IgG4 S228P subclass [REDACTED]

The therapeutic approach for the antibody SOL-116 is to block the function of BSSL in chronic inflammatory conditions with a lead indication to prevent inflammation and joint destruction in patients diagnosed with RA.

